### Secondary Outcomes

1. Quality of life: Assessed using the Functional Assessment of Cancer Therapy - Lung (FACT-L) and the Edmonton Symptom Assessment System (ESAS) questionnaires. [See Appendix 2, 3]
  - a. FACT-L: Rating questions regarding physical, social/family, emotion and function well-being as well as general questions regarding medical health, on a scale of 0-4 (from 'Not at all' to 'Very much').
  - b. ESAS: Rating pain, fatigue, nausea, depression, anxiety, drowsiness, appetite, well-being and shortness of breath, on a scale of 1 to 10.
2. Duration of indwelling chest tube catheter: In days, from insertion until removal of chest tube catheter.
3. Rate of screen failure: Proportion of participants who were screened, but did not meet one or more inclusion or exclusion criteria that was required for participation in the study.
4. Percent of eligible patients consented: Proportion of participants enrolled vs. not enrolled who meet all inclusion and exclusion criteria.

5. Pathway adherence rate: Proportion of participants enrolled that remained on the enhanced recovery pathway and followed all measures for same-day discharge vs. those that did not.

## 5.5 Statistical analysis

Participants that meet criteria (inclusion and exclusion) will be prospectively enrolled into this trial. Clinical data will be prospectively collected according to the Thoracic Surgery Quality monitoring, Information management, and Clinical documentation (TSQIC) software data management system and subsequently extracted for analysis; <https://tsqic.org/tsqic/>. [See Appendix 4]

Demographic characteristics (sex, age), baseline characteristics (past medical and surgical history, smoking status, occupational exposure), diagnostic data (pulmonary function [FEV1, FVC, DLCO], diagnosis, clinical staging), pathological data (pathological stage, margin status, lymphovascular invasion, pleural visceral invasion) and operative data (operative time, timing of surgery, morbidity and mortality including post-operative complications and major complications) will be collected.

*\*Post-operative complications:* recurrent pneumothorax, subcutaneous emphysema, prolonged air leak, pneumonia, pulmonary embolism, atrial fibrillation, bleeding, uncontrolled pain, chest tube reinsertion, wound infection, pleural empyema.

Complications will be scored using the Ottawa Thoracic Morbidity and Mortality classification system (15); <https://ottawatmm.org/>.

Clinical and pathological staging will be performed according to AJCC TNM 8th edition.

Specific research data, such as admission/discharge/emergency visit/readmission dates and secondary outcomes data, will be collected in a password-protected document behind the firewall of the MUHC. Only principal investigators and members of the research team will have access to the password.

Descriptive and observational sample analyses will be performed using proportions for categorical variables, means with standard deviations for normally distributed variables and medians with interquartile ranges (IQRs) for skewed distribution variables.

## 5.6 Benefits and risks

### *Benefits*

Participants may or may not personally benefit from their participation in this research study. The safety and feasibility information collected during the research will help guide future decisions with regards to implementing a same-day discharge ERP for patients undergoing VATS lung surgery.

### *Risks*

Although this protocol is designed and optimized to minimize any harm to the participants, there are possible risks related to the research procedures:

- ERP: unrecognized and more severe surgical complications (bleeding, urinary retention, arrhythmias, pneumothorax) requiring revisit to hospital
- Quality of life questionnaire: discomfort, distress
- Chest tube: inconvenience of returning for following on post-operative day 2, chest tube fall-out, wound care issues or infection

## **6.0 ETHICAL CONSIDERATIONS**

### **6.1 Consent**

Participants will be approached for consent during their pre-procedure (pre-op) visit. A detailed explanation of the study will be discussed including its purpose in regards to assessing the safety and feasibility of this enhanced recovery pathway. While the treating surgeon will be the one explaining the standard of care procedures in detail, the study details will be provided and consent obtained by the study's research coordinator. Consent will be documented by the participant's signed or verbal dated consent along with the signature of the person conducting the consent process and a witness, if applicable. A witness will be present for a verbal consent. The consent statement will be read aloud and participants will be given time to ask their questions. After verbal consent is given, the participants name, witness' name, and name of who is obtaining consent will be put on the informed consent document. No signatures will be collected for verbal consent. Verbal consent shall be collected if the participant has a reading disability or inability to read, communicates in a foreign language requiring an interpreter, or they are capable of consenting but unable to write. A copy of the consent form will be provided to the participant prior to participation in the study. A copy of the signed consent form should be given to the participant, or mailed to the participant's home address, if signature is required. For remote consent (over the phone), participants will receive a copy to sign when they arrive on site for their scheduled procedure.

The consent process will adhere to REB requirements, applicable laws and regulations including Health Canada's guidance on consent during the COVID-19 pandemic.

Should remote consent be required or requested, a digital copy of a signed consent form (photo or PDF) that has been emailed to the clinic will be accepted.

The total period of study for participant involvement will be approximately 2-3 months (surgical procedure + ERP + follow-up). The procedures and concepts included in the enhanced recovery pathway will be described and explained to the participant.

General participant information collected will include participants' demographic, diagnostic and pathological data. Information collected that is specific to this study will consist of adverse events and feasibility measures. All information will be de-identified to maintain participant confidentiality.

Study participation is completely voluntary. Patients may refuse participation or consent can be withdrawn at any time at the request of the participant without any consequence to their care.

### **6.2 Confidentiality**

This study will be conducted in accord with the Tri-Council Policy Statement: Ethical Conduct for Research Involving Humans (2018), as well as in respect of the requirements set out in the applicable standard operation procedures of the Research Institute of the McGill University Health Centre Research Institute and of the McGill University Health Centre Research Ethics Board. The McGill University Health Centre Research Ethics Board will review this study and will be responsible for monitoring it.

Only data relevant to this study as outlined in this protocol will be collected by the research team. All information collected during the research project will remain confidential to the extent required

and provided by law. Participant data will be de-identified and coded. The code will be kept by the Principal Investigator in a password-protected digital file behind the MUHC firewall.

Data may be published or shared during scientific meetings, however all participant identifying information will be excluded.

### **6.3 Maintenance of study records**

To enable evaluations and/or audits from regulatory authorities, the Principal Investigator agrees to keep records, including the identity of all participants, all original signed informed consent forms, source documents, and detailed records of treatment disposition.

The data will be entered in an electronic secure database (TSQIC) and file, which will be maintained with up-to-date information by the Principal Investigator or their team. It is the Principal Investigator's responsibility to ensure the accuracy of the data entered.

The clinical data extracted from TSQIC and research data collected will be de-identified and coded in a password protected file behind the MUHC firewall.

The data will be kept for a total of 7 years.

### **6.4 Compensation and reimbursement**

Participants will be compensated 50\$ for the additional follow-up visit after surgery, during which they will undergo removal of their chest tube. This compensation is provided by the Division of Thoracic Surgery Account.

### **6.5 Reporting Serious Adverse Events**

In compliance with SOP 405A.001 Serious Adverse Events (SAE) must be reported to the REB through NAGANO. Follow the guidelines below:

Local Serious Adverse Events:

- The Researcher must report to the REB any local serious adverse event that, in the opinion of the Researcher, meets all of the following criteria:
  - Unexpected;
  - Related or possibly related to participation in the research; and
  - Suggests that the research places research participants or others at a greater risk of harm than previously identified at time of review and approval.

Non-Local (External) Serious Adverse Events

- The Researcher must report to the REB, any non-local serious adverse event that, in the opinion of the Researcher, meets all of the following criteria:
  - Unexpected;
  - Related or possibly related to participation in the research; and
  - Suggests that the research places research participants or others at a greater risk of harm than previously identified at time of review and approval.

**AND**

  - Requires a change to the research and/or informed consent form and/or requires immediate notification to participants for safety reasons.

## Report to the REB

- The report submitted to the REB must include all of the following information:
  - The description of the adverse event;
  - Previous safety reports concerning similar events, if available;
  - An analysis of the significance of the current adverse event; and
  - If applicable, the proposed modifications to the conduct of the research project and/or to the informed consent form and/or a list of corrective actions to be taken in response to the event;
  - A copy of the sponsor's report, if available.
- Any applicable form completed/required by the sponsor, if any, (e.g. SAE form), must be uploaded to NAGANO
- Subsequent, important follow-up reports related to the SAE should be submitted as soon as available.

## 6.6 Stop Criteria

This pilot study will be halted if any of following criteria is met:

- >15% Grade 3 or 4 complications
- Any Grade 5 complications
- >10% readmission rate after 10 patients is discharged on same day

## Grading of Complications (17):

- Grade I: Any deviation from normal postoperative course without the need for pharmacological treatment or surgical, endoscopic, and radiological interventions.
- Grade II: Requiring pharmacological treatment with drugs other than such allowed for grade I complications. Blood transfusions and total parenteral nutrition are included
- Grade III: Requiring surgical, endoscopic or radiological intervention
- Grade IV: Life-threatening complications requiring IC/ICU management
- Grade V: Death of Patient

## **7.0 APPENDICES**

### **Appendix 1**

Perioperative anesthesia care pathway for same-day discharge anatomical lung or wedge resection feasibility study

SOC - Standard of care; RP – Research procedure

#### **A) PREOPERATIVE**

- All participants will be booked as the first case of the day to allow for a prolonged PACU stay, if needed. [RP]
- All participants will be flagged by a thoracic surgeon, and seen in the MGH preoperative clinic by an anesthetist. [SOC]
- All standard COVID-19 mitigation strategies for thoracic surgery patients will be employed. [SOC]
- Upon being called to OR, the participant will receive acetaminophen 1000 mg and celecoxib 200 mg PO with a sip of water. [SOC]
- Avoid routine use of midazolam. [SOC]

#### **B) INTRAOPERATIVE**

- Upon arrival to the operating room, preoperative checklist and consent will be verified. [SOC]
- Vascular access will be established and Ringer's Lactate will be started at 6 ml/kg/hour. [SOC]

Antibiotic prophylaxis:

- As per standard of care thoracic pathway. [SOC]

Monitoring:

- Standard monitoring will include ECG, arterial line, peripheral saturation, temperature, neuromuscular blockade at the adductor pollicis, lung mechanics and gas analyzer. [SOC]

Anesthesia:

- Inhalation anesthesia (sevoflurane or desflurane), or total intravenous anaesthesia (TIVA). [SOC]

Opioid-sparing analgesia (one or more of the following techniques):

- A preoperative single shot erector spinae plane nerve block will be performed at the T5 level with 20 ml of bupivacaine 0.375% with epinephrine 1:200 000, and dexamethasone 5 mg. [SOC]
- Magnesium sulfate 2.5 g IV will be given as co-analgesic over the course of the surgery. [SOC]
- Lidocaine 1.5 ml/kg following 2mg/kg/h. [SOC]
- Ketamine 0.5 mg/kg. [SOC]

Ventilation:

- Lung isolation will be performed with a left-sided double lumen endotracheal tube, or a bronchial blocker through a single-lumen tube. [SOC]

- Tidal volumes will be maintained at 6 ml/kg of PBW on 2 lungs and 4 ml/kg of PBW on one lung. PEEP and FiO2 will be adjusted to maintain SpO2 above 92%. Aim for driving pressure below 15 cmH2O. [SOC]

Temperature control:

- Normothermia will be maintained with an underbody heated water blanket on the operating table and a surgical access forced air warmer on the participant. [SOC]

Post-operative nausea and vomiting (PONV) prophylaxis:

- Dexamethasone 6 mg IV will be given at induction unless contraindicated. [SOC]
- Ondansetron 4 mg IV will be given 30 minutes before emergence of anesthesia. [SOC]
- Consider giving metoclopramide 10mg IV 30 minutes before emergence or use of TIVA if high PONV risk. [SOC]

End of surgery analgesia:

- At the end of the surgery, intercostal blocks will be performed by the surgeon, under direct visualization. A total a 20 ml of bupivacaine 0.25% with epinephrine 1:200,000 will be injected from T3 to T6. [SOC]

Extubation:

- At surgery completion, reverse neuromuscular blockade before extubating with suggamadex or neostigmine to achieve and document a ToF T4/T1 ratio > 0.9. [SOC]
- Participants will be extubated in the operating room and transferred to PACU. [SOC]

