**(b) Intraoperative ERP:**

- Proposed perioperative anesthesia care pathway consensus [See Appendix 1 for more details]. [SOC and RP]
- Extubation: In the operating room. [SOC]

**(c) Lung resection:** Patients will be placed under General Anesthesia and intubated with a double-lumen endotracheal tube. Patient will be rotated in lateral decubitus so as to elevate the surgical side (16). Standard sterilization and draping will be performed. A 3-5 cm incision will be performed in the fifth or fourth intercostal space and a 1cm incision in the eighth intercostal space. Some surgeons might choose to place a third access port that is 1-3 cm. The pleural cavity will be inspected and the site of tumor, identified. A segmentectomy or lobectomy will be performed in standard protocol. A 20F or 24F tube will be advanced to the thoracic apex and connected to Mini-Atrium dry seal drainage system (Mini-Atrium 500, Atrium, USA). Skin incisions will be closed in standard fashion. The procedures will be performed by staff surgeons from the Division of Upper Gastrointestinal and Thoracic Surgery. [SOC]

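### The lidocaine line in Appendix 1 gives a volume per kilogram with no concentration, so that quantity fixes no amount of drug

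*Protocol*

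**What the plan says.** Protocol section 5.3(b), Intraoperative ERP, sends the reader to Appendix 1 for the anaesthetic detail: "Proposed perioperative anesthesia care pathway consensus [See Appendix 1 for more details]. [SOC and RP". Appendix 1, part B, has a heading "Opioid-sparing analgesia (one or more of the following techniques", with four entries below it:

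- an erector spinae plane block using "20 ml of bupivacaine 0.375% with epinephrine 1:200 000", plus dexamethasone;
- "Magnesium sulfate 2.5 g IV will be given as co-analgesic over the course of the surgery";
- "Lidocaine 1.5 ml/kg following 2mg/kg/h";
- "Ketamine 0.5 mg/kg".

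All four carry the standard-of-care tag. Further down the same part, under end-of-surgery analgesia, a second local anaesthetic is given by volume: "20 ml of bupivacaine 0.25% with epinephrine 1:200,000 will be injected from T3 to T6".

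**The concern.** The lidocaine entry joins two quantities of different kinds, millilitres per kilogram and milligrams per kilogram per hour. Without a strength of solution, the first does not say how much drug is given. The neighbouring entries do not have this gap: where they use a volume they state a percentage, and otherwise they use a mass.

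There is a lesser point of order. In "following 2mg/kg/h", the linking word can be read as placing the hourly rate either before or after the per-kilogram quantity.

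What is at stake is patient safety. A team that selects lidocaine and works from the appendix cannot work out the amount of drug in the volume part. Following the line as written could give a wrong amount.

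**Working it through.** This is a check of dimensions. It involves no statistical input.

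**Inputs** (all from Appendix 1, part B)

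- Lidocaine: 1.5 ml/kg and 2 mg/kg/h. No concentration is stated, and this is the protocol's only mention of the drug.
- Bupivacaine, nerve block: 20 ml at 0.375%.
- Magnesium sulfate: 2.5 g.
- Ketamine: 0.5 mg/kg.
- Bupivacaine, intercostal blocks at the end of surgery: 20 ml at 0.25%.

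**Formula**

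Amount of drug = volume × concentration. A solution of p% holds p g per 100 ml, which is 10p mg/ml.

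**Entries that resolve**

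- Nerve block: 0.375% = 3.75 mg/ml, and 20 × 3.75 = 75 mg.
- Intercostal blocks: 0.25% = 2.5 mg/ml, and 20 × 2.5 = 50 mg.
- Magnesium and ketamine are already stated by mass.

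**Lidocaine**

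- Volume part: 1.5 ml/kg × c mg/ml = 1.5c mg/kg. The protocol never gives c, so the result is undefined.
- Rate part: 2 mg/kg/h is already a mass rate and needs no c.

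**Count**

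Of the four listed techniques, three define an amount of drug. Lidocaine's volume part is the exception. The intercostal blocks lie outside the list of four, but they show the same convention: where this part of the appendix gives a local anaesthetic by volume, it states the strength, except here.

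Part B also uses ml/kg for Ringer's Lactate and for tidal volumes. No mass of drug has to be derived in either case, so they are no precedent for the lidocaine entry.

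**How far the gap could reach**

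The concentrations below are assumptions chosen only to show scale. They are not in the protocol, and none is put forward as correct. The last column is 1.5c ÷ 2.

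| Assumed c (mg/ml) | 1.5c (mg/kg) | Equivalent hours at 2 mg/kg/h |
|---|---|---|
| 1 | 1.5 | 0.75 |
| 10 | 15 | 7.5 |
| 20 | 30 | 15 |

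Over this assumed range the same words cover a 20-fold span (30 ÷ 1.5). The conclusion does not depend on these values; it needs only that c is absent.

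**The case against.** The strongest reply concerns reach. The technique is one of four, of which a team uses one or more, so no participant has to receive lidocaine. The tag marks it as usual care, not a research procedure. Section 5.3 calls the pathway proposed. The study is a single-centre pilot of 20 participants, each seen before surgery by an anaesthetist, who may well know the intended local practice. No endpoint or analysis uses the line.

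All of this stands, and it limits how many participants could be affected. It does not repair the line. Elsewhere Appendix 1 defers openly: antibiotics and non-intravenous analgesia are referred to an existing pathway, and the oral opioid entry is marked as still to be standardised. The lidocaine entry makes no such deferral. It states a quantity, and the quantity is incomplete.

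A second reply is that a per-kilogram quantity and an hourly rate can be two separate components, so different units are not in themselves a contradiction. That is fair. The defect is the volume without a concentration, out of step with the rest of its own list; the hourly rate is not in question.

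A third is that the text was read by machine and the point turns on a single letter, ml against mg. Nothing in the passage suggests a misreading, and the nearby volumes read cleanly. A look at the source page would settle it.

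**Conclusion.** The concern holds. The volume part of the lidocaine entry defines no amount of drug: it equals 1.5c mg/kg with c stated nowhere in the protocol. The other three techniques in the list are each defined. The order of the two lidocaine quantities is unclear as a secondary matter. The only assumption is that the extracted text matches the source page.

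The point concerns patient safety alone and is confined to participants for whom lidocaine is chosen. It nevertheless needs correcting before use, because it is a drug quantity in the study's own anaesthetic pathway, in a study whose aim is to assess safety.

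**What to change.** Before the pathway is used, the investigators and the anaesthesia lead should check the lidocaine entry in Appendix 1, part B against the pathway it was taken from. They should reconcile its units, and restate it so that both quantities define an amount of drug and their order is plain. Which unit, concentration or dose is right is for them to settle; none is proposed here.

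The cost is the correction of one line in the appendix. Nothing changes in the sample size, outcomes, pathway-adherence measure or analysis.

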### **C) POST-OPERATIVE (IN PACU)**

Post-operative nausea and vomiting (PONV):

- Avoid dimenhydrinate IV/PO. [SOC]
- If nausea or vomiting occurs within 6 hours after surgery, participants should not receive a repeat dose of the prophylactic antiemetic received intra-operatively. Treat with one of the following instead: [SOC]
  - Ondansetron 4 mg IV
  - Metoclopramide 10 mg IV
  - Haloperidol 0.5-1 mg IV/IM

Fluids:

- Clear fluids PO as tolerated. [SOC]
- Ringer's Lactate IV at 10 mL/h ("Keep Vein Open" - KVO). [SOC]

Analgesia:

- Fentanyl 25 mcg IV to a maximum of 250 mcg. [SOC]
- Non-IV analgesia as per pathway. [SOC]
- Oxycodone 5mg PO q2h PRN or Dilaudid 1mg PO q2h PRN (to be standardized). [SOC]
- Acetaminophen 1000 mg PO/PR q6h regular to be started 6h after the first dose. [SOC]

Respiratory support:

- Incentive spirometry in PACU. [SOC]
- Possible physiotherapy in PACU. [SOC]

## Appendix 2

Example of Functional Assessment of Cancer Therapy - Lung (FACT-L) questionnaire in English and French

### FACT-L (Version 4)

Below is a list of statements that other people with your illness have said are important. **Please circle or mark one number per line to indicate your response as it applies to the past 7 days.**

PHYSICAL WELL-BEING		Not at all	A little bit	Some- what	Quite a bit	Very much
GP1	I have a lack of energy .....	0	1	2	3	4
GP2	I have nausea .....	0	1	2	3	4
GP3	Because of my physical condition, I have trouble meeting the needs of my family .....	0	1	2	3	4
GP4	I have pain .....	0	1	2	3	4
GP5	I am bothered by side effects of treatment .....	0	1	2	3	4
GP6	I feel ill .....	0	1	2	3	4
GP7	I am forced to spend time in bed .....	0	1	2	3	4

SOCIAL/FAMILY WELL-BEING		Not at all	A little bit	Some- what	Quite a bit	Very much
GS1	I feel close to my friends .....	0	1	2	3	4
GS2	I get emotional support from my family .....	0	1	2	3	4
GS3	I get support from my friends.....	0	1	2	3	4
GS4	My family has accepted my illness .....	0	1	2	3	4
GS5	I am satisfied with family communication about my illness.....	0	1	2	3	4
GS6	I feel close to my partner (or the person who is my main support) .....	0	1	2	3	4
Q1	Regardless of your current level of sexual activity, please answer the following question. If you prefer not to answer it, please mark this box  and go to the next section.					
GS7	I am satisfied with my sex life .....	0	1	2	3	4

